11.2.1 Medical history

Standard medical history, with special attention for:

- ♦ WHO performance status
- ♦ Toxicities
- ♦ Infections

Only at entry:

- ♦ Prior and present other diseases
- ♦ Antecedent hematological or oncological diseases
- ♦ Previous chemotherapy

11.2.2 Physical examination

Standard physical examination including body weight and height, with special attention for:

- ♦ Spleen size in cm below mid left costal margin
- ♦ Toxicities
- ♦ Infections

11.2.3 Hematology

Complete hematogram with special attention for:

- ♦ Hemoglobin
- ♦ WBC
- ♦ WBC differential count including description of circulating erythroblasts, reticulocytes
- ♦ Platelet count
- ♦ Recovery of peripheral blood cells after cycle I and II (arm B)

11.2.4 Blood chemistry

- ♦ BUN
- ♦ Creatinine
- ♦ ASAT (SGOT)
- ♦ ALAT (SGPT)
- ♦ Alkaline phosphatase
- ♦ γ -GT
- ♦ Total bilirubin
- ♦ LDH

11.2.5 Bone marrow

- ♦ Bone marrow biopsy at entry for histology including reticulin stain (Gomori's stain)
- ♦ Bone marrow aspirate for cytology and differential
- ♦ Bone marrow aspirate for cytogenetic analysis as described in 11.2.6

In addition to these investigations, all patients are asked for informed consent to store biological material at entry, 6 and 12 months after entry and at progression, for future studies. These studies include proteomic and genomic analysis to identify potential biomarkers predictive of response and

progression-free survival. All materials are anonymized and stored for a maximum of 15 years after inclusion has been completed, after which the samples will be destroyed. Any study to be undertaken on these materials must be approved of by the study coordinators and relevant ethical authorities prior to undertaking the studies.

11.2.6 Cytogenetic analysis

- ◆ Conventional cytogenetic analysis of at least 20 metaphases
- ◆ FISH analysis for Philadelphia chromosome (optional)

11.2.7 Molecular analysis (see also appendix C)

- ◆ At entry real-time quantitative PCR for bcr-abl on both bone marrow and peripheral blood samples
- ◆ Real-time quantitative PCR for bcr-abl on both bone marrow and peripheral blood samples at 3, 6 and 12 months after entry (Arm A)
- ◆ Real-time quantitative PCR for bcr-abl on both bone marrow and peripheral blood samples after cycles I and II and at 6 and 12 months after entry (Arm B)
- ◆ Real-time quantitative PCR for bcr-abl on peripheral blood samples during monotherapy and follow up every 6 months after entry starting at 12 months after entry

11.2.8 Specific investigations

- ◆ Ultrasonogram spleen and liver (size in cm)
- ◆ X-Thorax
- ◆ ECG

11.2.9 Additional investigations

- ◆ HLA-typing (A, B) for platelet transfusions
- ◆ Platelet antibodies: auto and (optional) allo
- ◆ Neutrophil alkaline phosphatase score (optional)

11.2.10 Additional investigations during cytarabine treatment

- ◆ Platelet count, WBC and differential at least 2-3 times weekly
- ◆ BUN, creatinine, sodium, potassium, calcium, glucose daily during chemotherapy, and thereafter at least twice weekly
- ◆ ALAT, ASAT, alkaline phosphatase, γ -GT, bilirubin and LDH at least weekly
- ◆ Routine urine analysis weekly
- ◆ X-Thorax once during the first week, thereafter as clinically indicated

11.3 Evaluation of response

Response will be evaluated according to the criteria in appendix C. Response will be assessed after cycle I (arm B), after cycle II (arm B), after 3 months (arm A) and thereafter approximately every 6

months during imatinib monotherapy and follow up starting at 6 months after entry.

12 Toxicities

All chemotherapeutic agents used in the protocol can cause pancytopenia and can induce septic or hemorrhagic complications.

Cytarabine can cause anorexia, nausea, vomiting, hepatic dysfunction, skin rash, pneumonitis, fever.

Imatinib can cause nausea, muscle spasms, arthralgia, headache, peri-orbital edema and liverfunction abnormalities.

Toxicities will be scored according to the NCI Common Terminology Criteria for Adverse Events, version 3.0 (see appendix D).

13 Reporting serious adverse events

Adverse event (AE)

An adverse event (AE) is any untoward medical occurrence in a patient or clinical study subject during protocol treatment. An AE does not necessarily have a causal relationship with the treatment. An AE can therefore be any unfavorable and unintended sign (including an abnormal laboratory finding), symptom, or disease temporally associated with the use of a medicinal (investigational) product, whether or not related to the medicinal (investigational) product.

Adverse reaction (AR)

Adverse reactions (AR) are those AE's of which a reasonable causal relationship to any dose administered of the investigational medicinal product and the event is suspected.

Serious adverse event (SAE)

A serious adverse event is defined as any untoward medical occurrence that at any dose results in:

- death
- a life-threatening event (i.e. the patient was at immediate risk of death at the time the reaction was observed)
- hospitalization or prolongation of hospitalization
- significant / persistent disability
- a congenital anomaly / birth defect
- any other medically important condition (i.e. important adverse reactions that are not immediately life threatening or do not result in death or hospitalization but may jeopardize the patient or may require intervention to prevent one of the other outcomes listed above)

Note that ANY death, whether due to side effects of the treatment or due to progressive disease or due to other causes is considered as a serious adverse event.

Unexpected SAE

Unexpected Serious Adverse Events are those SAE's of which the nature or severity is not consistent with information in the relevant source documents. For a medicinal product not yet approved for marketing in a country, a company's Investigator's Brochure will serve as a source document in that country.

Suspected unexpected serious adverse reaction (SUSAR)

All suspected AR's which occur in the trial and that are both unexpected and serious.

Protocol treatment period

The protocol treatment period is defined as the period from the first study-related procedure until 30 days following the last dose of protocol treatment or until the start of another systemic anti-cancer treatment off protocol, if earlier.

13.2 Reporting of (serious) adverse events

Adverse event

AE's will be reported on the CRF. All adverse events of Grade 2 or higher, with the exception of progression of disease, occurring during the protocol treatment period will be reported. Adverse events occurring after that period should also be reported if considered related to protocol treatment.

SAE and Unexpected serious adverse event

All SAE's occurring during the protocol treatment period must be reported to the HOVON Data Center by fax **within 24 hours of the initial observation of the event**, except hospitalizations for:

- a standard procedure for protocol therapy administration. Hospitalization or prolonged hospitalization for a complication of therapy administration will be reported as a Serious Adverse Event.
- the administration of blood or platelet transfusion. Hospitalization or prolonged hospitalization for a complication of such transfusion remains a reportable serious adverse event.
- a procedure for protocol/disease-related investigations (e.g., surgery, scans, endoscopy, sampling for laboratory tests, bone marrow sampling). Hospitalization or prolonged hospitalization for a complication of such procedures remains a reportable serious adverse event.
- prolonged hospitalization for technical, practical, or social reasons, in absence of an adverse event.
- a procedure that is planned (i.e., planned prior to starting of treatment on study; must be documented in the CRF). Prolonged hospitalization for a complication considered to be at least possibly related to the protocol treatment remains a reportable serious adverse event.

All details should be documented on the **Serious Adverse Event and Death Report**. In circumstances where it is not possible to submit a complete report an initial report may be made giving only the mandatory information. Initial reports must be followed-up by a complete report within a further 2 working days and sent to the HOVON Data Center. All SAE Reports must be dated and signed by the responsible investigator or one of his/her authorized staff members.

At any time after the protocol treatment period, *unexpected* Serious Adverse Events that are considered to be at least suspected to be related to protocol treatment must also be reported to the HOVON Data Center using the same procedure, **within 24 hours after the SAE was known to the investigator**.

The investigator will decide whether the serious adverse event is related to the treatment (i.e. unrelated, unlikely, possible, probable, definitely and not assessable) and the decision will be recorded on the serious adverse event form. The assessment of causality is made by the investigator using the following:

RELATIONSHIP	DESCRIPTION
UNRELATED	There is no evidence of any causal relationship to the protocol treatment (also include pre-existing conditions)
UNLIKELY	There is little evidence to suggest there is a causal relationship (e.g. the event did not occur within a reasonable time after administration of the trial medication). There is another reasonable explanation for the event (e.g. the patient's clinical condition, other concomitant treatments).
POSSIBLE	There is some evidence to suggest a causal relationship (e.g. because the event occurs within a reasonable time after administration of the trial medication). However, the influence of other factors may have contributed to the event (e.g. the patient's clinical condition, other concomitant treatments).
PROBABLE	There is evidence to suggest a causal relationship and the influence of other factors is unlikely.
DEFINITELY	There is clear evidence to suggest a causal relationship and other possible contributing factors can be ruled out.
NOT ASSESSABLE	There is insufficient or incomplete evidence to make a clinical judgement of the causal relationship.

13.3 Processing of serious adverse event reports

The HOVON Data Center will forward all reports within 24 hours of receipt to the study coordinator and the study central datamanager. The report of an SAE will be the signal for the central datamanager to ask the investigator or the responsible local datamanager to complete and send as soon as possible all relevant CRF's for the involved patient with details of treatment and outcome.

14 Endpoints

Primary endpoint

1. Rate of major molecular response at 12 months from randomization.

Secondary endpoints

2. Rate and duration of major and complete molecular response;
3. Rate and duration of major and complete cytogenetic response;
4. Rate and duration of complete hematological response;
5. Progression-free survival (i.e. time from registration to progression or death from any cause, whichever occurs first);
6. Overall survival measured from the time of registration. Patients still alive or lost to follow up are censored at the date they were last known to be alive;
7. Toxicity;
8. Actual dose-intensity of imatinib delivered;
9. Incidence of mutations of abl-kinase domain.

15 Data collection

Data will be collected on Case Report Forms (CRF) to document eligibility, safety and efficacy parameters, compliance to treatment schedules and parameters necessary to evaluate the study endpoints. Data collected on the CRF are derived from the protocol and will include at least:

- ♦ inclusion and exclusion criteria;
- ♦ baseline status of patient including medical history and stage of disease;
- ♦ timing and dosage of protocol treatment;
- ♦ adverse events;
- ♦ parameters for response evaluation;
- ♦ any other parameters necessary to evaluate the study endpoints;
- ♦ survival status of patient;
- ♦ reason for end of protocol treatment.

Each CRF page will be identified by a pre-printed trial number, and a unique combination of patient study number (assigned at registration), hospital and patient namecode (as documented at registration) to be filled out before completing the form.

The CRF will be completed on site by the local investigator or an authorized staff member. Each page must be dated and signed by the local investigator upon completion. All CRF entries must be based on source documents. The CRF and written instructions for completing the CRF will be provided by the HOVON Data Center.

Copies of the CRF will be kept on site. The original CRF pages must be sent to the HOVON Data Center at the requested timepoints. How and when to send in forms is described in detail in the CRF

header and the CRF instructions.

All data from the CRF will be entered into the study database by the HOVON Data Center.

16 Randomization

Eligible patients should be registered within 2 months of diagnosis. Patients can be registered at the HOVON Data Center of the Erasmus MC – Daniel den Hoed by phone call: [name] or [contact] Monday through Friday, from 09:00 to 17:00, or via the Internet through TOP (Trial Online Process; <https://www.hdc.hovon.nl/top>). A logon to TOP can be requested at the HOVON Data Center for participants.

The following information will be requested at registration:

- ◆ Protocol number
- ◆ Institution name
- ◆ Name of caller/responsible investigator
- ◆ Patient's initials or code
- ◆ Patient's hospital record number (optional)
- ◆ Sex
- ◆ Date of birth
- ◆ Date of diagnosis CML
- ◆ Eligibility criteria

All eligibility criteria will be checked with a checklist. Patients will be randomized, stratified by center and Sokal score with a minimization procedure, ensuring balance within each stratum and overall balance. The randomization result and a unique patient study number will be given immediately by TOP or phone and confirmed by fax or email.

17 Statistical considerations

17.1 Sample size and power considerations

This study is designed to establish whether addition of two 7-days' cycles of cytarabine 200 mg/m²/day to daily imatinib 800 mg treatment, will improve outcome as compared to treatment with 800 mg imatinib daily alone.

Results in 114 newly diagnosed chronic phase CML patients who were treated with monotherapy imatinib 800 mg daily (Kantarjian; Blood 2004; 103:2873-2878) suggest 1-year major molecular response (MMR) of about 60% and a 1-year complete molecular response (CMR) of 25-30%. This is much higher than obtained in the IRIS-study (Hughes; NEJM 2003; 349:1423-1432), where imatinib 400 mg daily resulted in about 40% MMR and about 5% CMR at 12 months.

Data on imatinib treatment combined with two 7-days' cycles of cytarabine are only available from the HOVON 51 CML-trial. The primary goal of this trial was to investigate the feasibility of imatinib treatment (between 200 and 800 mg daily) combined with 2 cycles of cytarabine (200 or 1000 mg/m²/day) in 7 different combinations. Preliminary data available as of September 2005 have confirmed the feasibility of the first 6 dose levels; data of the highest dose level are currently awaited.

A secondary end point of this trial was MMR. Combined for all dose levels, an actuarial estimate of the overall MMR at 12 months of about 53% was achieved, with a standard error (s.e.) of 5%. Moreover, a failure rate of 8% (s.e. 3%) was observed, while 38% (s.e. 5%) of all patients neither had a MMR nor a failure (acceleration, blastic crisis or death within 12 months). An actuarial 12-months MMR rate of 76% was seen in those patients with imatinib 800 mg/day, as compared to about 40% in patients treated with 400 mg/day, which confirmed the results of Hughes and Kantarjian, which established the choice for imatinib 800 mg/day in both treatment arms for the current trial. Whether cytarabine 200 mg/m²/day is better than no cytarabine at all is not clear, and will therefore be evaluated in this trial. It should be noted that preliminary results of about 68 patients in the HOVON 51 CML-trial (daily imatinib 800 mg, dose levels IV A and V) showed an actuarial 12-months' MMR of 76% (s.e. 10%) and a 12-months' CMR of 41% (s.e. 12%).

Data from the IRIS-study show the impact of MMR, as they did not observe any progression of death in patients who were in MMR at 12 months, for a follow up period of 12-18 months. However, because long-term follow up data of patients who achieve a MMR are lacking, we will consider MMR at 12 months as the primary end point for this trial.

Patients who have achieved a MMR at 12 months after randomization, will be considered a success. Patients will be considered a failure in case of:

- ◆ loss of hematological, cytogenetic or molecular response, accelerated phase, blastic crisis, clonal evolution or death before 12 months;
- ◆ no MMR achieved within 12 months.

In order to detect with 80% power an improvement in 12-months' MMR from 60% to 75% (2-sided significance level $\alpha=0.05$), 330 patients are required. This will be achieved in about 5 years, as an accrual of 60-70 patients per year is expected.

17.2 Statistical analysis

All analyses will be according to the intention to treat principle.

17.2.1 Efficacy analysis

The main endpoint for the comparison between the two treatment arms is the proportion of patients

with a MMR at 12 months. The proportions will be compared between the two treatment arms using logistic regression. In addition, an exploratory logistic regression with adjustment for baseline Sokal score will be performed to evaluate the effect of Sokal score on the MMR rate at 12 months.

Secondary end points include the rates of hematological response, complete cytogenetic response (CcyR), major molecular response (MMR) and complete molecular response (CMR), time to CcyR, MMR and CMR, progression-free survival and overall survival from randomization.

Actuarial survival curves for all time-to-event end points will be computed using the Kaplan-Meier method, 95% confidence intervals will be constructed, and survival curves will be compared using the log-rank test for illustrative purposes, without and with stratification based on the Sokal score.

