7.1 Registration, randomization and study treatment

Patients with newly diagnosed CML, Philadelphia-positive or bc/abl positive, in first chronic phase meeting all eligibility criteria (see section 8.1) and having provided informed consent will be randomized between:

- Arm A: imatinib given orally at a total dose of 800 mg daily until progression
- Arm B: imatinib given orally at a total dose of 800 mg daily, combined with 2 successive cycles of i.v. cytarabine 200 mg/m², at day 1-7, in cycles I and II, followed by imatinib monotherapy (800 mg daily) until progression

Treatment according to study arms A or B will start following cessation of preceding therapy with hydroxyurea (HU) or cessation of preceding therapy with imatinib. Preceding therapy with HU is allowed for no longer than 2 months and preceding therapy with imatinib is allowed for no longer than 1 month.

8 Study population

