11.1 Time of clinical evaluations

Arm A:

- ◆ At entry: before start imatinib*
- ◆ ≤ 12 months from entry: at 3, 6 and 12 months after start imatinib
- ◆ > 12 months from entry: every 6 months
- ◆ Follow up: every 6 months

Arm B:

- ◆ At entry: before start imatinib*
- ◆ After cytarabine cycle I: approximately 4 weeks after start cycle I
- ◆ After cytarabine cycle II: approximately 4 weeks after start cycle II

- ◆ Imatinib monotherapy: every 6 months, with the first clinical evaluation at 6 months after entry
- ◆ Follow up: every 6 months

* For patients treated with imatinib prior to entry in the study baseline evaluations are those performed before start imatinib, if available. If unavailable, baseline evaluations should be performed at entry.

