Hematological response

Complete hematological remission

Requires all of the following:

- ♦ Normalization of leukocyte count: $WBC < 10 \times 10^9/l$;
- ♦ Normal differentials without circulating immature forms; a percentage of circulating immature cells $\leq 2\%$ is compatible with complete hematological remission, provided that it concerns no immature forms other than myelocytes and metamyelocytes:
blasts = 0%, promyelocytes = 0%, myelocytes+metamyelocytes $\leq 2\%$;
- ♦ Normalization of platelet count: platelets $< 450 \times 10^9/l$;
- ♦ Disappearance of all clinical symptoms and signs of disease including palpable splenomegaly.

Partial hematological remission

Not fulfilling all the criteria for complete hematological remission, with $WBC \leq 20 \times 10^9/l$.

Failure

$WBC > 20 \times 10^9/l$, or progression of disease to accelerated phase or blastic crisis without prior complete hematological remission.

Cytogenetic response

At least 20 metaphases analysed by conventional cytogenetic analysis or 200 metaphases/interphases analysed by FISH.

Complete: Ph^+ chromosomes = 0%

Partial: Ph^+ chromosomes $> 0\%$ and Ph^+ chromosomes $< 35\%$

Minimal: Ph^+ chromosomes $\geq 35\%$ and Ph^+ chromosomes $< 100\%$

Absent: Ph^+ chromosomes = 100%

Patients with either complete or partial cytogenetic response are considered to have achieved a major cytogenetic response.

Molecular response

Complete response: ≥ 4.5 log decrease of bcr-abl mRNA detectable by real-time quantitative RT-PCR

Major Response: ≥ 3 log decrease of bcr-abl mRNA detectable by real-time quantitative RT-PCR

Partial Response: ≥ 1 log and < 3 log decrease of bcr-abl mRNA detectable by real-time quantitative RT-PCR

No response: < 1 log decrease of bcr-abl mRNA detectable by real-time quantitative RT-PCR

Molecular responses will be monitored by means of real-time quantitative RT-PCR for the bcr-abl fusion transcript. Protocols for real-time quantitative RT-PCR for bcr-abl will be standardized by the Dutch Network for Molecular Diagnostics. Quality control will also be performed under the supervision of the Dutch Network for Molecular Diagnostics.

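### The primary logistic regression of 12-month MMR has no term for baseline bcr-abl, which is scheduled at entry in both arms; adding it is a cheap efficiency gain of uncertain size, not the repair of an error

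*Protocol*

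**What the plan says.** The primary endpoint in Section 14 is "Rate of major molecular response at 12 months from randomization". On its analysis, Section 17.2.1 says: "The proportions will be compared between the two treatment arms using logistic regression". No covariate is named. The same section then adds that "an exploratory logistic regression with adjustment for baseline Sokal score will be performed", in order to look at the effect of Sokal score on the response rate. Because adjustment is set apart as additional and exploratory, the primary model is treatment only. That is a stated choice, not a detail left open.

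Appendix C defines MMR as at least a "3 log decrease of bcr-abl mRNA detectable by real-time quantitative RT-PCR". It does not say from which reference level the decrease is counted.

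Section 11.2.7 schedules the same measurement before treatment: "At entry real-time quantitative PCR for bcr-abl on both bone marrow and peripheral blood samples". The table in Section 11.2 and Appendix C agree, for both arms.

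Section 7.1 states that "preceding therapy with imatinib is allowed for no longer than 1 month". For such patients, Section 11.1 and footnote 1 of the table in Section 11.2 take the evaluations made before imatinib as baseline where they exist, and otherwise: "If unavailable, baseline evaluations should be performed at entry".

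Section 16 minimises on centre and Sokal score, not on bcr-abl level.

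**The concern.** A pre-treatment value of the outcome's own measurement is usually the first candidate for a covariate, and here it is already scheduled. If it predicts 12-month MMR, a treatment-only model leaves that variation unexplained and has somewhat less power than an adjusted one. Chance differences between the arms in starting level are balanced neither by the minimisation nor by the model.

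At stake is precision. Neither the validity of the test nor the type I error is in question.

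**Working it through.** **1. The plan's own figure.** Inputs from Section 17.1: 60% versus 75%, two-sided alpha 0.05, power 80%, N=330. Section 17.4 (75 per arm among the first 150) implies 1:1 allocation.

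Uncorrected size per arm, with pooled rate 0.675:

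n = [1.96·√(2·0.675·0.325) + 0.8416·√(0.60·0.40 + 0.75·0.25)]² / 0.15² = (1.298 + 0.550)² / 0.0225 ≈ 151.9, that is 152 per arm, 304 in total.

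With continuity correction: (151.9/4)·[1 + √(1 + 4/(151.9·0.15))]² ≈ 164.9, that is 165 per arm, **330 in total**. The stated figure is reproduced exactly.

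Power of the uncorrected test at 165 per arm: Φ[(0.15·√165 − 1.298)/0.654] = Φ(0.961) = **83.2%**.

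**2. Power with a baseline covariate.** The protocol gives no association between entry bcr-abl and MMR, so its strength is assumed and varied. Simulation with 5,000 trials per row: 165 per arm, a standard normal covariate, overall rates held at 60% and 75%, Wald test from logistic regression without and with the covariate. Simulation error is about 0.5 points on each power, so the differences within the unadjusted column are noise around 83%.

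| Odds ratio per SD of covariate | Unadjusted | Adjusted | Gain (points) | Conditional treatment OR |
|---|---|---|---|---|
| 1.0 | 83.98% | 83.96% | 0.0 | 2.00 |
| 1.25 | 83.00% | 83.42% | 0.4 | 2.02 |
| 1.5 | 82.20% | 83.54% | 1.3 | 2.05 |
| 2.0 | 83.88% | 86.18% | 2.3 | 2.14 |
| 2.5 | 83.56% | 88.52% | 5.0 | 2.24 |
| 3.0 | 83.52% | 89.86% | 6.3 | 2.34 |

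The unadjusted odds ratio is (0.75/0.25)/(0.60/0.40) = 2.00.

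A second simulation, with 6,000 trials per setting, treats MMR as a threshold on a normal log decrease correlated with log10 entry level:

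| Correlation | Unadjusted | Adjusted | Gain (points) |
|---|---|---|---|
| 0.2 | 83.4% | 84.4% | 1.0 |
| 0.3 | 84.2% | 85.6% | 1.4 |
| 0.4 | 83.6% | 87.0% | 3.4 |
| 0.5 | 83.3% | 89.4% | 6.1 |

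**3. How large might the correlation be?** Suppose the decrease is counted from the patient's own baseline. Let B be the SD of log10 entry level, M the SD at month 12, and r the correlation between the two levels. The correlation of entry level with log decrease is

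(B − r·M) / √(B² + M² − 2·r·B·M).

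With assumed SDs B = 0.5 and M = 0.8 or 1.2:

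- r = 0: 0.5/√0.89 = 0.53, or 0.5/√1.69 = 0.38
- r = 0.3: 0.26/√0.65 = 0.32, or 0.14/√1.33 = 0.12
- r = 0.5: 0.10/√0.49 = 0.14, or −0.10/√1.09 = −0.10

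So the 5 to 6 point gain needs the month-12 level to be nearly unrelated to the entry level and the month-12 spread to be at the low end. With r of 0.3 or 0.5 the gain is about 1.5 points or less.

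If the decrease is instead counted from a common laboratory reference, response depends on the month-12 level alone. The correlation is then −r, and the gain is zero when r is zero.

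**The case against.** The strongest case against is that nothing is wrong. An unadjusted comparison in a randomised trial is valid, its type I error already allows for chance imbalance in any baseline variable, and 330 was sized for exactly this comparison with power to spare. All of that stands. A reader might infer from the missing covariate that the trial is underpowered or its primary test faulty; Section 17.1 does not support that.

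A reader might also take MMR to be a fall from each patient's own entry level, so that a low start leaves less room to fall. Appendix C names no reference. Under a common reference a low start would make MMR easier to reach, so even the direction of the relation is open. The case for adjustment must rest on possible prognostic value, not on that mechanism.

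The pretreatment example is weaker than it looks, because Section 11.1 prefers the pre-imatinib sample. Only patients without one have an on-treatment baseline. Entry PCR is also scheduled, which is not the same as obtained in everyone.

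The second simulation makes MMR a pure threshold on log decrease, whereas Section 17.1 also counts death, acceleration, blastic crisis, clonal evolution and loss of response as failures. The first simulation models overall success directly and gives gains of the same order.

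Finally, Sokal score and centre have a better documented claim as covariates, being the minimisation factors. That is a reason to revisit the same sentence of Section 17.2.1, not an argument against adding baseline bcr-abl.

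What survives is narrow. Within simulation error, adjusted power was never below unadjusted power in any setting, and the data are already scheduled.

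**Conclusion.** The point holds as a minor, optional improvement. The treatment-only primary model is valid and has about 83% power against a target of 80%. Adding baseline bcr-abl would raise power by:

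- 0 to about 1.5 points if entry level is weakly prognostic (odds ratio per SD up to 1.5, or latent correlation up to 0.3);
- about 2 to 3 points if moderate (odds ratio 2, or correlation 0.4);
- 5 to 6 points only if strong (odds ratio 2.5 to 3, or correlation 0.5).

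The protocol does not show which of these applies, and zero cannot be excluded. Quoting 6 points as the expected gain would overstate the case. So would saying that power is given up at no cost, since adjustment changes the odds ratio being estimated and needs rules for the baseline sample and for missing values.

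**What to change.** In Section 17.2.1, before any comparison by arm is seen, state that:

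- the primary logistic regression includes treatment and log10 baseline bcr-abl as a continuous covariate;
- the baseline comes from one named source, blood or marrow (both are assayed at entry and at month 12), following the rule of Section 11.1: pre-imatinib sample if available, otherwise the entry sample;
- a missing baseline is handled by a missing-value indicator or by single imputation from baseline data only, so that every randomised patient stays in the intention-to-treat analysis;
- the unadjusted odds ratio and the difference in proportions are reported beside the adjusted result.

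The cost is a few lines of analysis text and no new data. There are two downsides. The adjusted odds ratio is conditional: over the range above, an unadjusted 2.00 corresponds to 2.05 to 2.34 for covariate odds ratios of 1.5 to 3, which is why the unadjusted measures should be shown with it. And the covariate is an on-treatment value in those pretreated patients who have no pre-imatinib sample, which should be acknowledged in the report.
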